Title	Can High-Intensity Interval Training (HIIT) reduce the risk of diabetes relapse following discharge from the NHS Path to Remission Programme? – a pilot study
Short title	HIIT post LCD
Chief Investigator	[name]
Objectives	To determine the effect of a 16-week home-based HIIT intervention on markers of glucose metabolism and glycaemic control in individuals with T2D that have achieved diabetes remission in the NHS Path to Remission Programme.
Trial Configuration	Parallel group, non-blinded, randomised control study
Setting	Clinical research facility (Postgraduate Centre, University of Nottingham, Derby Campus)
Sample size estimate	This is a pilot study, therefore no power calculation has been performed
Number of participants	20 participants will be recruited and allocated 1:1 into intervention or control groups
Eligibility criteria	
 • Adults between the age of 18-70 years • Ability to provide informed consent. • Completed the NHS Path to Remission programme and achieved diabetes remission (HbA1c <48mmol/mol (6.5%), and off diabetes medications for at least three months)
Description of interventions	The intervention group will participate in a 16-week HIIT programme involving 3 sessions per week in their own homes. The HIIT sessions are comprised of five 1-minute intervals of body-weight exercises interspersed with 90-second active recovery periods. The control group will continue with their usual levels of activity.
Duration of study	
Each participant will be involved in the study for 16 weeks.
 
The study is expected to commence in November 2024 and be completed by the end of August 2026.

Randomisation and blinding	Participants will be randomised to the two groups using the “sealed envelope” online software. Research staff in direct contact with participants will not be blinded, however staff involved solely in analysis of samples and data will be blinded to the randomisation of participants.
Outcome measures	
The primary endpoint for this study will be beta-cell function assessed during an intravenous glucose tolerance test (IVGTT)
 
Secondary outcome measures include:
 
 • Insulin sensitivity • Overall glycaemic control • Body weight • Body composition • Skeletal muscle function

	
 • Skeletal muscle structure • Cardiorespiratory fitness (measured as VO_{2max} during cardiopulmonary exercise testing, CPET)

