TRIAL / STUDY CONFIGURATION

This study will be a single-centre, randomised, non-blinded physiological study.

Primary endpoint

The primary endpoint for this study will be pancreatic beta cell function, determined as the incremental suprabasal insulin concentration during the first 10 minutes of an intravenous glucose tolerance test (IVGTT)

Secondary endpoints

1. Insulin sensitivity – measured during the intravenous glucose tolerance test (IVGTT) and calculated from fasting glucose and insulin using the homeostatic model of assessment for insulin resistance
2. Overall glycaemic control – assessed from measurement of glycated haemoglobin (HbA1c)
3. Body weight
4. Body composition – deduced from bioimpedance analysis (BIA)
5. Skeletal muscle function – assessed using muscle strength testing and electromyography
6. Skeletal muscle structure – using muscle ultrasonography
7. Cardiorespiratory fitness – determined from be the highest rate of oxygen consumption obtained (VO_{2max}) during a cardiopulmonary exercise test (CPET)

Safety endpoints

HIIT is well known to be a safe intervention in individuals with T2D. Therefore, as such, there are no safety endpoints in this study.

However, the safety of participants in the study will be rigorously maintained. Participants will be monitored during the study days for any adverse events associated with any of the procedures performed. In particular, participants will be monitored extensively during the CPET with continuous heart rate, blood pressure, pulse oximetry and electrocardiogram (ECG) monitoring throughout. Each CPET session will be supervised by members of the research team, one of which is a medically trained clinician who will be present throughout the session. In the unlikely event of a participant requiring urgent medical attention, initial first aid will be provided and emergency services contacted if required. Our department has conducted multiple studies in which CPETs are performed and has no incidences of adverse events during these assessments.

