Following this, the participant will be laid on a clinical examination bed in the reclined position in preparation for the IVGTT. Initially, an intravenous cannula will be inserted into the participants arm (by a trained clinical practitioner from within the research team) and fasting blood tests will be obtained. Another blood test for glucose and insulin will be obtained from the cannula 5-10 minutes later, and immediately after this, an intravenous bolus of 20% glucose will be administered, signifying the start of the IVGTT. The dose of 20% glucose administered will be calculated as 0.5g/kg body weight (up to a maximum of 35g i.e. 175ml of 20% glucose), as per standard IVGTT protocol (Bingley *et al.*, 1992). This calculation will be performed by the Co-Investigator [name], who is experienced in calculations of infusion doses. Blood samples for glucose and insulin will be obtained at 2, 4, 6, 8, 10, 20, 30, 40, 50 & 60 minutes after the initial glucose bolus. The IVGTT is a well-established method for measuring insulin sensitivity and pancreatic beta cell function (Cersosimo *et al.*, 2014; Hannon *et al.*, 2018) and has been widely utilised in studies investigating a range of exercise interventions (Slentz *et al.*, 2009; Gillen *et al.*, 2016; Mora-Rodriguez *et al.*, 2019). A total of 50ml of blood will be drawn from the participants during the IVGTT. During the IVGTT, an ultrasound of the right vastus lateralis will be performed to assess muscle cross sectional area, fascicle length and pennation angle. Additionally, participants will be asked to complete questionnaires gathering information regarding their current physical activity and quality of life.

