Data will be analysed within our research department based in the Division of Medicinal Sciences and Graduate Entry Medicine, at the Royal Derby Hospital campus of the University of Nottingham. Analysis will be performed primarily by [name], under the supervision of Chief Investigator and other Co-Investigators. In addition, there will be oversight provided by the university support statistician. It will not be possible to blind the study investigators to the randomisation of participants. However, staff involved solely in analysis of samples and data will be blinded to the randomisation of participants. All analysed data will be stored and backed-up within a secure online data management system on the University of Nottingham's internal server.

Data will be analysed using the statistical programmes GraphPad Prism v10.2.1 (La Jolla, California, the USA), which is available on the university internal server. Prior to statistical analysis, data will be tested for normality using the Kolmogorov-Smirnov test. Normally distributed data will be expressed as mean (SD), whilst non-normally distributed data will be reported as median \pm inter-quartile range.

The primary endpoint beta-cell function will be derived from the area-under-curve (AUC) of serum insulin concentration during the first 10 minutes of the IVGTT (Cersosimo *et al.*, 2014). This correlates well with the gold standard hyperinsulinaemic clamp (Rakotoambinina *et al.*, 1997) and can sensitively detect changes in beta cell function in response to dietary interventions (Jackness *et al.*, 2013; Liu *et al.*, 2015). Insulin sensitivity will be derived from serum glucose and insulin concentrations obtained during the IVGTT. An insulin sensitivity index developed by Tura *et al.* (Tura *et al.*, 2010) will be calculated, as well as HOMA2-IR from fasting glucose and insulin concentrations. Body composition measures (lean body mass and fat mass) will be directly determined from BIA.

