Two-way analysis of variance (ANOVA) will be used to determine statistically significant differences between the mean baseline and follow-up measurements of all outcomes in both groups. Additionally, the independent samples t-test will be used to compare mean changes in outcomes between the two groups and test for statistical significant differences between them. Non-parametric alternatives will be used if data are non-normally distributed. If, despite randomisation, the mean value of an outcome at baseline is different between the groups then linear regression analysis will be performed to account for the baseline difference. The significance level will be set at $p=0.05$.

Interim analysis of available data will be performed 8-10 months into the course of the study, in order to inform the funding organisation that progress is being made. Finally, in order to maintain the safety of participants, the occurrence of adverse events will be continuously monitored and if an unacceptably high incidence of such events is noted, this will be highlighted to the Chief Investigator and Co-Investigators. At this point, a decision will be made regarding continuation of the study, or if other safety procedures are required to reduce the AE occurrence rate.

Sample size and justification

This is a pilot study, as such, no power calculation has been performed to justify sample size. However, a previous study with similar participant numbers has successfully demonstrated significant improvements in beta-cell function following a HIIT intervention (Madsen *et al.*, 2015b).

Assessment of efficacy

The primary endpoint for this study is pancreatic beta-cell function assessed during an IVGTT. Thus, the HIIT intervention will be deemed efficacious if participants in the intervention group have a significantly higher beta-cell function than those in the control group, i.e. there is a greater improvement in insulin response to intravenous glucose after the 16-week intervention than after 16 weeks of usual care. Significant difference will be determined using two-way ANOVA (or other more appropriate statistical tests) as outlined above.

The secondary endpoints will provide evidence of the efficacy of the HIIT intervention on inducing improvements in other measures of cardiometabolic health and are listed below:

- Improvement in insulin sensitivity suggested by increased insulin sensitivity index (derived from the IVGTT) and reduced HOMA2-IR

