- Improvement in overall glycaemic control – reduced HbA1c, reduced fasting glucose, reduced fasting insulin
- Reduced body weight
- Improved body composition – reduced fat mass and increased lean body mass
- Increased muscle strength and muscle function during electromyography, gait and balance analysis

- Increased fascicle length and greater pennation angle in the vastus lateralis muscle (determined by ultrasonography)
- Improved cardiorespiratory fitness – determined by increased VO_{2max} during CPET

Assessment of safety

Safety of participants will be actively monitored throughout the course of the study. Participants will be contacted regularly through the 16-week study to determine occurrence of adverse events. These will be documented in the participant's case report form and in the trial master file. There will also be a database specifically designated to the documentation of adverse events and safety concerns. This database will be reviewed regularly by the Chief Investigator and Co-Investigators. If there is a high occurrence of adverse events then this will be discussed and considerations made about altering the protocol to counteract this. If the occurrence becomes unacceptably high then the study will be terminated before completion.

Procedures for missing, unused and spurious data

This is a small research study, therefore missing data would have a significant impact on the validity of the results obtained. As such, every effort will be made to ensure the amount of missing data is kept to a minimum. Study visits will be performed by researchers who have a full and complete understanding of every aspect of the study. There will be a detailed proforma with clear instructions regarding the data that are to be collected at each timepoint. In addition, any samples requiring storage prior to analysis will be duplicated and stored in separate freezers.

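### The primary endpoint is insulin above basal in the design section but an insulin AUC with no stated basal subtraction in the statistics section; read literally, the two differ by 10 minutes times fasting insulin

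*Protocol*

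**What the plan says.** The protocol describes the primary endpoint in four places.

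- **Trial / Study Configuration, Primary endpoint:** beta-cell function is "determined as the incremental suprabasal insulin concentration during the first 10 minutes of an intravenous glucose tolerance test (IVGTT". This is insulin above the basal level. The section does not say whether the increment is summarised as an area, a mean or a peak.
- **Statistics, Methods:** "The primary endpoint beta-cell function will be derived from the area-under-curve (AUC) of serum insulin concentration during the first 10 minutes of the IVGTT". This names a summary form (area) and the same 10-minute window, but says nothing about removing the basal level.
- **Synopsis:** "The primary endpoint for this study will be beta-cell function assessed during an intravenous glucose tolerance test (IVGTT". No metric is given.
- **Assessment of efficacy:** HIIT is judged efficacious if "there is a greater improvement in insulin response to intravenous glucose after the 16-week intervention" than after usual care. Again no metric is named.

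Two further statements bear on the point. Assessment of efficacy lists among the expected improvements "reduced HbA1c, reduced fasting glucose, reduced fasting insulin", and also "increased insulin sensitivity index (derived from the IVGTT) and reduced HOMA2-IR"; HOMA2-IR is calculated from fasting glucose and insulin. Under First study visit, fasting bloods are drawn and then "Another blood test for glucose and insulin will be obtained from the cannula 5-10 minutes later", immediately before the glucose bolus, so a basal insulin value will be available.

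**The concern.** One statement of the primary variable removes fasting insulin. The other, taken at its word, leaves it in. The Synopsis and the efficacy criterion name no metric, so neither expressly settles the matter.

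The difference could affect the result because the protocol expects treatment to move fasting insulin. If HIIT lowers fasting insulin, an AUC that includes the basal level falls with it, and part of a hypothesised secondary benefit is scored as poorer beta-cell function. An AUC above basal is not affected in this way.

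The trial has 20 participants, and efficacy is judged by significance at the 0.05 level. Staff who work only on analysis are blinded, but the investigators who supervise the analysis are not, and an interim look at the data is planned at 8–10 months. A primary variable that can be read in two ways leaves a choice open after data have been seen. The results are also meant to inform larger studies, which will need to know which variable was measured.

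**Working it through.** **Inputs from the protocol.** The window is 0–10 minutes, with insulin sampled before the bolus and at 2, 4, 6, 8 and 10 minutes. Fasting insulin is expected to fall under HIIT. The protocol states no insulin level, effect size, SD or power, so there is no figure of its own to reproduce.

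**Assumed inputs, for illustration only.** Fasting (basal) insulin B is 60–100 pmol/L. Incremental AUC over 0–10 minutes, I, is 1000–2500 pmol/L·min. The fall in fasting insulin, f, is 10–30%.

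**Step 1: how the two readings are related.** A constant basal level contributes a rectangle of height B and width 10 minutes:

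total AUC = I + 10 × B

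change in total AUC = change in I + 10 × change in B

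The two readings therefore differ by 10 × B at each visit, and their changes differ by 10 times the change in fasting insulin.

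**Step 2: share of total AUC that is basal,** 10B / (I + 10B), and **Step 3: percentage fall in total AUC when B falls by f and I is unchanged,** f × 10B / (I + 10B). At the four corners of the assumed ranges:

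| B | I | 10B | Total AUC | Basal share | f = 10% | f = 20% | f = 30% |
|---|---|---|---|---|---|---|---|
| 60 | 1000 | 600 | 1600 | 37.5% | 3.8% | 7.5% | 11.3% |
| 60 | 2500 | 600 | 3100 | 19.4% | 1.9% | 3.9% | 5.8% |
| 100 | 1000 | 1000 | 2000 | 50.0% | 5.0% | 10.0% | 15.0% |
| 100 | 2500 | 1000 | 3500 | 28.6% | 2.9% | 5.7% | 8.6% |

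For example, with B = 60, I = 2500 and f = 20%, total AUC goes from 3100 to 2980, and 120 / 3100 = 3.9%. With B = 100, I = 1000 and f = 20%, it goes from 2000 to 1800, and 200 / 2000 = 10%. The incremental AUC changes by 0 in every cell.

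Over the whole grid the basal share is 19–50%. The fall in total AUC is about 4–10% for f = 20%, and 2–15% for f between 10% and 30%.

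**Step 4: when the two readings point in opposite directions.** If I rises by a fraction g while B falls by f, total AUC still falls whenever g is below

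g* = f × 10B / I

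Over the assumed ranges 10B / I runs from 600/2500 = 0.24 to 1000/1000 = 1.0. For f = 20%, g* is therefore between 0.20 × 0.24 = 4.8% and 0.20 × 1.0 = 20%. A true gain in the insulin response smaller than g* would appear as a loss on total AUC. A larger gain keeps its sign but is understated.

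**The case against.** The strongest reply is that the two passages are complementary. The design section fixes the quantity (insulin above basal) without a summary form. The statistics section supplies the form (an area over the same window) and says only that the endpoint is derived from it. It never says total AUC. Read together they give incremental AUC. The efficacy criterion supports this, since it speaks of the response to intravenous glucose and fasting insulin is not such a response. So does the insulin sample taken just before the bolus. This stands as evidence of probable intent. It does not make the statistics section say so, and an analyst working from that section alone would compute an area that contains the fasting level.

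A second reply is that computational detail belongs in a statistical analysis plan, which is not at hand. That holds for the integration rule and for how basal samples are combined. It does not cover whether the basal level is removed, because the protocol itself describes the primary variable twice and the descriptions differ on exactly that.

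A reader might go further and infer that the planned analysis is biased against HIIT, or that the conclusion would probably reverse. The documents do not support either. Bias requires that total AUC actually be used and that fasting insulin actually fall. The size depends on insulin values the protocol does not give. Where the response is large relative to basal, the effect is small: at 10B / I = 0.24, even a 30% fall in fasting insulin is cancelled by a 7.2% gain in the response (0.30 × 0.24). The protocol also speaks of preventing deterioration, which could happen with little change in fasting insulin. A reader might likewise infer that total AUC would credit controls whose fasting insulin rises with weight regain. The protocol mentions regain only as a general risk after intensive caloric restriction and does not say that it is expected within 16 weeks.

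**Conclusion.** The point holds as an inconsistency in the definition of the primary variable. One section specifies insulin above basal; the other specifies an insulin AUC without stating basal subtraction. Subtraction may well have been intended, but the literal readings differ by 10 minutes times fasting insulin, a quantity the protocol expects HIIT to reduce.

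That the wording differs does not depend on any assumption. The consequence is conditional: if the literal AUC were used, and if fasting insulin fell by 20% with the incremental response unchanged, the primary variable would fall by about 4–10% on the illustrative values above, against no change in the incremental AUC.

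Pilot status and the lack of a power calculation limit what rides on the result. They do not remove the need for a single primary variable when efficacy is to be declared by a significance test in 20 people. Having the basal-corrected version stated prospectively in the design section limits later choice but does not close it off.

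**What to change.** Amend Statistics, Methods to agree with the Primary endpoint section. State that the primary variable is the area under the serum insulin curve from 0 to 10 minutes of the IVGTT above basal, and say how basal is defined, for example as the mean of the pre-bolus samples already scheduled under First study visit. Use the same definition in the Synopsis, the Primary endpoint section (which at present names no summary form) and Assessment of efficacy. If total AUC is reported at all, label it a sensitivity analysis.

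The cost is about one sentence, repeated where the endpoint is described. All the samples needed are already in the visit schedule, and no visit or sample-size figure changes. The amendment should be made before the planned interim analysis, so that the definition is settled before any outcome data are examined.

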- Completed the NHS Path to Remission programme and achieved diabetes remission (HbA1c <48mmol/mol (6.5%), and off diabetes medications for at least three months)

Exclusion criteria

- BMI > 40kg·m²
- Current participation in a formal exercise regime
- Current pregnancy or breastfeeding
- Uncontrolled hypertension (blood pressure >160/100mmHg)
- History of cardiovascular disease:
 - Symptomatic angina
 - Heart failure (class III/IV)
 - Significant arrhythmias
 - Right to left cardiac shunt
 - Recent acute coronary syndrome
 - Severe aortic valvular disease
 - Active cardiac infection
- Background of the following respiratory diseases:

- Pulmonary hypertension
- Significant COPD
- Uncontrolled asthma
- History of malignancy undergoing current treatment or palliation
- Presence of significant musculoskeletal, neurological or cerebrovascular disease
- Any other medical condition deemed by the investigators to preclude inclusion into the study

These exclusion criteria are based on the contraindications listed in the American Thoracic Society / American College of Chest Physicians statement on CPET (ATS/ACCP, 2003).

Expected duration of participant participation

Study participants will be participating in the study for 16 weeks.

Removal of participants from therapy or assessments/Participant Withdrawal

Participants may be withdrawn from the trial either at their own request or at the discretion of the Investigator. The participants will be made aware that this will not affect their future care. Participants will be made aware (via the information sheet and consent form) that should they withdraw the data collected to date cannot be erased and may still be used in the final analysis.

Participants may be removed temporarily or permanently depending on the prevailing circumstances around the time of the decision. Grounds for temporary removal from the study include (but are not limited to):

- very mild joint or limb injury (not requiring medical attention)
- inability to continue with the exercise intervention due to unforeseen personal circumstances (e.g. bereavement)

Participants will be permanently removed from the study in the following situations:

- withdrawal of consent
- significant injury (requiring medical attention)
- development of any high-risk symptoms (listed above in the Exclusion Criteria section) whilst performing any of the home-based exercise sessions
- evidence of high-risk signs (listed above) during the CPET sessions

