- failure to achieve minimum compliance with the exercise intervention

If a participant withdraws their consent after screening but before the first study visit, they may be replaced. Should a participant withdraw during or following the first study-visit, they will not be replaced, and instead, will be deemed to have dropped out of the study. As randomisation will occur immediately before the participant's first study visit, anyone who withdraws after randomisation will also be classed as a drop-out from the study.

For participants that are removed from the study, details of this decision will be documented in the CRF. The date and time of removal will be documented, as well as the reason for doing so (if provided). A decision to remove any participant that is made by the research team, will be discussed with the Chief Investigator and will require final agreement by them. We do not envisage any potential issues with abrupt withdrawal from the study and therefore, do not have measures to prevent any issues. Participants that are withdrawn will be advised to continue their care arrangements with their General Practitioner, and a letter will be sent to the General Practitioner informing them of the individual's participation in the study – in the same way as for all participants who complete the study.

Informed consent

All participants will provide written informed consent. The Informed Consent Form will be signed and dated by the participant before they enter the trial. The Investigator will explain the details of the trial and provide a Participant Information Sheet, ensuring that the participant has sufficient time to consider participating or not. The Investigator will answer any questions that the participant has concerning study participation.

Informed consent will be collected from each participant before they undergo any interventions (including physical examination and history taking) related to the study. One copy of this will be kept by the participant, one will be kept by the Investigator, and a third will be retained in the patient's hospital records.

Should there be any subsequent amendment to the final protocol, which might affect a participant's participation in the trial, continuing consent will be obtained using an amended Consent form which will be signed by the participant.

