The control group will not be participating in any exercise intervention. Participants in this group will be instructed to make no significant changes to their current levels of physical activity for the 16-week period.

All participants will be advised to continue their regular medications as prescribed. These regular medications will have been recorded at the screening appointment and documented in the CRF.

Final Visit

At the end of the 16 weeks (approximately 72 hours after their final HIIT session), all participants will undergo their final study visit. This will follow the exact same format of the first study visit, except at the end of this study visit participants will be asked to complete a feedback questionnaire, thanked for their involvement and exited from the study. Subsequently, their General Practitioner will be sent a letter detailing their results with a copy also sent directly to them. If participants have any questions regarding their results and ongoing management, they will be advised to discuss these with their General Practitioner.

Compliance

Participants in the intervention group will be asked to complete an exercise documentation pack, in which they will be required to record details of each exercise session performed. They will be contacted by phone (or email) at regular intervals (at least weekly) and compliance will be one of the issues discussed, with reference to their documentation pack.

Participants will be expected to perform the HIIT sessions 3 times per week. However, this can be increased to 4 times if a session has been missed from the previous week. Compliance will be deemed acceptable if >80% of sessions are performed. Participants will be excluded if they:

- are unable to complete 4 or more consecutive sessions
- miss more than 7 sessions in total
- fail to complete the set exercise regime in 7 or more sessions

The number of participants excluded due to poor compliance will be recorded and reported in the study report and any potential publications.

Criteria for terminating trial

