With these measures in place, we will endeavour to ensure that less than 10% of the data set will be missing. If this is achieved, the data will be analysed using standard statistical techniques as described above. However, if despite these measures there is greater than 10% missing data, this will be discussed directly with the support statistician and the procedure for dealing with this will then depend on the extent of data that is missing. Techniques such as imputation will be considered if required, however if analysis can be performed without the need for such techniques then this would be the preferred option.

If it is not possible to perform an IVGTT in a particular participant (e.g. due to difficulty obtaining vascular access), no data regarding the primary outcome will be collected for that participant. In this situation, data will still be collected for the remaining secondary outcomes during the first visit. Moreover, the participant will be permitted to participate in the 16-week intervention (or control) period and the second visit will be conducted, however without the repeat IVGTT. In order to ensure the target number of participants is reached, with regard to the primary outcome, an additional participant will be recruited for every participant that cannot complete the IVGTT.

Definition of populations analysed

Full Analysis set: All randomised participants, who participated in at least one HIIT session and for whom at least one post-baseline assessment of beta-cell function is available.

Per protocol set: All participants in the Full Analysis set who are deemed to have no major protocol violations that could interfere with the objectives of the study.

ADVERSE EVENTS

Definitions

An adverse event is any unfavourable and unintended sign, symptom, syndrome or illness that develops or worsens during the period of observation in the study.

An AE does include a / an:

1. exacerbation of a pre-existing illness.
2. increase in frequency or intensity of a pre-existing episodic event or condition.
3. condition detected or diagnosed after medicinal product administration even though it may have been present prior to the start of the study.
4. continuous persistent disease or symptoms present at baseline that worsen following the start of the study.

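### HIIT participants who fail compliance or have symptoms at home sessions leave the study, not just the exercise, so the HIIT arm is selected after randomisation in a way the control arm cannot be

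*Protocol*

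**What the plan says.** The Protocol section on removal and withdrawal has therapy and assessments in its title, but its text treats them as one. It states: "Participants will be permanently removed from the study in the following situations". The grounds include withdrawal of consent, significant injury needing medical attention, high-risk signs during CPET, and these two:

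- "development of any high-risk symptoms (listed above in the Exclusion Criteria section) whilst performing any of the home-based exercise sessions"
- "failure to achieve minimum compliance with the exercise intervention"

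The Compliance section sets the exclusion triggers (consecutive sessions, total sessions missed, incomplete sessions) and adds: "The number of participants excluded due to poor compliance will be recorded and reported in the study report and any potential publications".

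Other parts of the protocol fix what removal means for the data:

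- The regimen has one outcome visit after baseline, at week 16, and the duration section plans no follow-up after it.
- Anyone who withdraws after randomisation counts as a drop-out and is not replaced.
- The Full Analysis Set is limited to participants with a post-baseline assessment of beta-cell function.
- The missing-data section aims for less than 10% missing and refers anything above 10% to the support statistician. Imputation may be considered, but "if analysis can be performed without the need for such techniques then this would be the preferred option".

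Nothing in the protocol asks a removed participant to attend week 16.

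**The concern.** Compliance and tolerance of home sessions are observed after randomisation, and only in the arm that exercises. If failing on either costs a participant the week-16 IVGTT, the HIIT arm in the primary analysis consists of those who adhered and tolerated the programme. The control arm passes no such filter, so the two groups are no longer comparable by randomisation.

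Two uses of the result are at stake. The efficacy section will call HIIT efficacious on a significant between-group difference in beta-cell function. The background section says the results will inform larger studies of real-world use, which need the effect of offering the programme to everyone eligible, including those who do not keep it up. A statistical analysis plan, if one exists, can choose an estimator, but it cannot analyse IVGTTs that were never performed. The data-collection rule has to be changed in the protocol.

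**Working it through.** **Inputs from the protocol.** The synopsis states "20 participants will be recruited and allocated 1:1 into intervention or control groups", which is 10 per arm. On power: "This is a pilot study, as such, no power calculation has been performed to justify sample size". No SD, effect size or drop-out rate is given, so there is no planned figure to reproduce. The significance level is 0.05, taken here as two-sided.

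**Which grounds fall on which arm.**

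| Ground for permanent removal | HIIT | Control |
|---|---|---|
| Failed compliance | yes | cannot occur |
| Symptoms in home sessions | yes | cannot occur |
| Injury needing medical attention | yes, expected more often | possible as worded |
| High-risk CPET signs | yes | yes |
| Withdrawal of consent | yes | yes |

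**Size of the shift (assumptions, not protocol figures).** Take a true HIIT effect of zero. Let k of the 10 HIIT participants be removed, with correlation r between outcome and adherence. The planned t-test on change was simulated 100,000 times per setting.

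| Removed | r | Shift towards HIIT (SD) | False positives favouring HIIT (nominal 2.5%) |
|---|---|---|---|
| 2 of 10 | 0 | 0.00 | 2.5% |
| 2 of 10 | 0.3 | 0.10 | 3.8% |
| 2 of 10 | 0.5 | 0.16 | 5.2% |
| 3 of 10 | 0 | 0.00 | 2.5% |
| 3 of 10 | 0.3 | 0.14 | 4.6% |
| 3 of 10 | 0.5 | 0.23 | 6.6% |

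As a cross-check, the large-sample formula r·φ(z_q)/(1−q) gives 0.350r at q = 0.2 and 0.497r at q = 0.3. With r = 0.3 to 0.5 that is 0.105 to 0.175 and 0.149 to 0.248 SD, slightly above the simulated values for an arm of 10.

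**If HIIT does work, but only in those who do it.** The completer effect divided by the as-randomised effect is 1/(1−q): 1/0.8 = 1.25 with 20% removed and 1/0.7 = 1.43 with 30% removed. Completers would overstate the effect of offering the programme by 25% to 43%.

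**Precision.** The 95% CI half-width in SD units is t(0.975, n₁+n₂−2)·√(1/n₁+1/n₂).

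- 10 v 10: 2.101 × 0.447 = 0.94
- 8 v 10: 2.120 × 0.474 = 1.01
- 7 v 10: 2.131 × 0.493 = 1.05

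**Whether the missing-data rule would catch it.** The denominator is not defined. Three removals are 3/20 = 15% of participants, above the 10% trigger, but 3/40 = 7.5% of participant-visits, below it. On the second count the standard analysis runs with no further step.

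**Consistency of the compliance rule.** 16 weeks × 3 = 48 sessions. With 8 missed, 40/48 = 83.3% are performed; with 9 missed, 39/48 = 81.3%. Both exceed the 80% the protocol calls acceptable, and both exceed the limit of 7 missed sessions that triggers exclusion.

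**The case against.** Several points on the other side are fair.

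- **Not every ground is one-sided.** A reader might infer that only HIIT participants can be removed. The text does not support that: the injury ground is not limited to HIIT, and CPET signs apply to both arms. The asymmetry is exact for compliance and home-session symptoms only.
- **The direction is not certain.** A reader might treat bias towards HIIT as established. It requires removed participants to do worse, or gain less, than those who stay. The correlation and removal rates are assumed, and how injury or symptoms relate to insulin response is unknown.
- **Removal is partly discretionary.** The stopping-rules section says removal for symptoms will be considered. Very mild injury or personal circumstances lead only to temporary removal, a missed session can be made up the following week, and removals by the team need the Chief Investigator's agreement. This may lower the number removed but does not change what removal does to the data.
- **The plan does not rule out imputation.** It prefers to avoid it and consults the statistician above 10%. Neither route recovers an outcome that was not collected.
- **This is a small, unpowered pilot that reports compliance exclusions.** The illustrated shift is well inside the confidence half-width. But the protocol still ties an efficacy claim to the comparison, and a count of exclusions shows the problem without correcting it.

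A reader might also expect a large loss of precision. One-arm loss takes the half-width from 0.94 to only 1.01 or 1.05 SD.

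**Conclusion.** The concern holds for the two grounds that only the HIIT arm can meet: failed compliance and symptoms in home sessions. Injury probably adds to it, but the wording does not confine injury to HIIT. Followed as written, the plan produces a HIIT arm selected on post-randomisation adherence and tolerance, and no later analysis can restore the missing week-16 values.

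Bias towards HIIT is expected rather than proven. Under the stated assumptions (no true effect, correlation 0.3 to 0.5) it is about 0.10 to 0.16 SD with 2 of 10 removed and 0.14 to 0.23 SD with 3 of 10. It vanishes at zero correlation. The precision loss is modest, and bias is the main issue.

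**What to change.** 1. Separate stopping HIIT from leaving the study, and delete compliance failure as a ground for removal from assessments.
2. Invite to week 16 every randomised participant who still consents and whom the investigator judges safe to assess under the existing safety rules, for whichever of IVGTT, HbA1c, weight and BIA are appropriate. The safety condition covers the IVGTT as well as any exercise test. Partial visits have a precedent: the missing-data section already keeps participants without an IVGTT in the study for the other outcomes.
3. Analyse by allocated group. Use compliance only to define the Per Protocol set and as a reported adherence outcome.
4. Leave the rules for stopping exercise unchanged, but reconcile the passages that disagree: removal for symptoms is to be considered in the stopping-rules section but mandatory in the withdrawal section; the withdrawal section points to the exclusion criteria for a symptom list that stands under the stopping rules; and the 80% rule conflicts with the limit of 7 missed sessions at 8 or 9 missed of 48.

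The cost is protocol and PIS wording, plus a few final visits for participants who stopped HIIT, within the visit schedule already planned. If all those removed attend, the comparison stays 10 v 10 and this source of bias disappears. Participants who withdraw consent or cannot safely be assessed will still be missing and should be reported by arm and reason.
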